## List of Abbreviations

[figure not shown]
AU	Aarhus University
AUH	Aarhus University Hospital
3BNC117	Anti-HIV-1 bNAbs targeting the CD4 binding site of gp120
Ab	Antibody
AE	Adverse Event/Adverse Experience
ART	Antiretroviral Therapy
ATI	Analytic Treatment Interruption
bNAbs	Broadly Neutralizing Antibodies
CD4	T-cell Surface Glycoprotein CD4
CFR	Code of Federal Regulations
cGMP	Current Good Manufacturing Practices
CONSORT	Consolidated Standards of Reporting Trials
CRF	Case Report Form
CRSO	Clinical Research Support Office
CTSA	Clinical and Translational Science Award
CCTS	Center for Clinical and Translational Science
CU	Cologne University
CUH	Cologne University Hospital
DC	Dendritic Cell
DNA	Deoxyribonucleic Acid
DSMB	Data and Safety Monitoring Board
FDA	Food and Drug Administration
FWA	Federal-Wide Assurance
GCP	Good Clinical Practice
gp120	HIV-1 Envelope Glycoprotein 120
HDAC	Histone deacetylase
HIPAA	Health Insurance Portability and Accountability Act
HIV-1	Human immunodeficiency virus
hu-mice	Humanized Mice
IB	Investigator's Brochure
ICF	Informed Consent Form
ICH	International Conference on Harmonization
I.M.	Intramuscularly
IND	Investigational New Drug
IRB	Institutional Review Board
I.V.	Intravenously
N	Number (typically refers to participants)
NIAID	National Institute of Allergy and Infectious Diseases, NIH
NIH	National Institutes of Health
OHRP	Office for Human Research Protections
OHSR	Office for Human Subjects Research
PBMC	Peripheral Blood Mononuclear Cell
PI	Principal Investigator
RU	The Rockefeller University
RUH	The Rockefeller University Hospital
QA	Quality Assurance
QC	Quality Control
RNA	Ribonucleic Acid
SAE	Serious Adverse Event/Serious Adverse Experience
S.C.	Subcutaneously
SHIV	Chimeric Simian/Human Immunodeficiency Virus
SOP	Standard Operating Procedure
T cell	T lymphocyte
V3 loop	Third Variable Loop of the HIV-1 Virion Envelope Glycoprotein 120

**Study Schema**

Title	A phase 2a, randomized study of romidepsin with or without 3BNC117 to evaluate the effects on the HIV-1 reservoir (ROADMAP)
Short Title	Romidepsin plus 3BNC117 phase 2a study
Protocol Number	MCA-896
Phase	Phase 2a
IND Sponsor	The Rockefeller University
Study Center(s)	The Rockefeller University (RUH; Coordinating Site), New York, NY, U.S.A. University Hospital of Cologne, Cologne, Germany Aarhus University Hospital, Aarhus, Denmark
Principal Investigators	[name], [name] PhD, [name]
Study Design	
This is a randomized interventional phase 2a trial of 3BNC117 and romidepsin in HIV-1-infected patients on ART, conducted as a multi-center study at the Department of Infectious Diseases, Aarhus University Hospital, Denmark, the Rockefeller University Hospital, USA, and the University Hospital of Cologne, Germany.
 
Participants will be randomized 1:1 in a non-blinded fashion to receive one of two regimens:
 
A) Two treatment cycles each consisting of one 3BNC117 infusion (30mg/kg) + three romidepsin infusions (5mg/m^2); or
 
B) Two treatment cycles each consisting of three romidepsin infusions (5mg/m^2).
 
ART will be discontinued 16 weeks after the start of the second treatment cycle (analytical treatment interruption, ATI) and subjects will be monitored weekly for safety and viral rebound. The study outline is shown in Figure 1. The targeted enrolment is 30 subjects (15 per arm).
 
Leukapheresis will be performed before and after the two treatment cycles to guarantee sufficient material to investigate changes in the reservoir after the interventions.

Figure 1. Study Design:

The following criteria will require resumption of ART:

- CD4+ T cell-count <350 cells/mm^3 (confirmed by repeat measurement)
- 2 consecutive plasma HIV-1 RNA measurements ≥ 200 copies/mL or above their setpoint viremia (if documented)
- Subject request
- Continued ART interruption will, in the opinion of the investigator or study advisers, pose an unacceptable risk to the subject.

If HIV-1 RNA remains undetectable at week 36, subjects will be offered to continue off ART with close monitoring, in conjunction with the subject’s primary medical provider, as long as HIV-1 viral rebound does not occur. ART resumption will follow same criteria as detailed above. All subjects will be followed for a total of 48 weeks from enrollment.

Study Duration	50 weeks per participant; total planned study duration 24 months
Objectives	
Primary Objective:
 
 
- Evaluate the effects of romidepsin plus 3BNC117 or romidepsin alone on delaying or preventing viral rebound in HIV-1-infected individuals during an analytical interruption of ART.
 
 
Secondary Objectives:
 
 
- Evaluate the safety of romidepsin plus 3BNC117 or romidepsin alone in ART-treated HIV-1 infected individuals;
 
- Evaluate the effects of romidepsin plus 3BNC117 or romidepsin alone on the size of the replication competent HIV-1 reservoir in ART-treated HIV-1-infected individuals;
 
- Evaluate the immunomodulatory effects of romidepsin plus 3BNC117 or romidepsin alone in ART-treated HIV-1-infected individuals.
 

Number of Subjects	30 (15:15)

Study Population	HIV-infected males and females, between the ages of 18-65, on ART for at least 24 months, with HIV-1 RNA plasma level of < 50 copies/ml by standard assays for at least 18 months, and with current CD4+ T cell counts > 500 cells/ $\mu$ l.
Inclusion / Exclusion Criteria	
Inclusion Criteria:
 
 
1. Adults age 18-65 years with documented HIV-1 infection
 
2. CD4+ T-cell count >500 cells/mm^3 at screening
 
3. On ART for a minimum of 18 months and HIV-1 RNA plasma level of < 50 copies/ml by standard assays for at least 12 months (a single viral load measurement > 50 but < 500 copies/ml during this time period is allowable).
 
4. Individuals on protease inhibitor or NNRTI-based regimens, or regimens containing cobicistat must be willing to switch to an integrase-inhibitor-based regimen (raltegravir or dolutegravir) prior to enrollment.
 
 
Exclusion Criteria:
 
 
1. Use of systemic corticosteroids, immunosuppressive anti-cancer, or other medications considered significant by the investigators within the last 6 months
 
2. Pregnancy as determined by a positive urine or serum beta-hCG.
 
3. Participant unwilling to use two reliable contraception methods (i.e. condom with spermicide, diaphragm with spermicide, progestin-only containing intrauterine device (IUD) (eg, Mirena, Implanon), non-estrogen containing formulations of hormonal birth control drugs with condom) for the study duration. Romidepsin may interact with estrogen-based contraceptives and such agents may be unreliable in participants receiving romidepsin.
 
4. Currently breast-feeding.
 
5. History of resistance to 2 or more classes of antiretroviral medications
 
6. Any medical, psychiatric, social, or occupational condition that, as judged by the investigators, would interfere with the evaluation of study objectives (such as severe alcohol or drug abuse, dementia).
 
7. Acute or chronic hepatitis B or C infection as indicated by the presence of Hepatitis B surface antigen (HBsAg) or hepatitis C virus RNA (HCV-RNA) in blood.
 
8. A history of AIDS-defining illness within 3 years prior to enrollment.
 
9. History of B-cell lymphoma, including CNS lymphoma
 
10. CD4 nadir < 200 cells/mm^3 within the last 5 years.
 
11. History of significant coronary artery disease, myocardial infarction, percutaneous coronary intervention with placement of cardiac stents, or family history of sudden death at age < 50 years.
 
12. ECG at screening that shows QTc >450 msec when calculated using the Fridericia formula from either lead V3 or V4, pathological Q-waves (Q-wave > 40 msec or depth > 0.4-0.5 mV), evidence of a ventricular pre-excitation syndromes, complete or incomplete LBBB or RBBB, second or third degree heart block, QRS duration > 120 msec, or bradycardia defined by sinus rate < 50 bps
 
13. Use of QT-prolonging medication, renal or hepatic disease, structural heart disease or left ventricular dysfunction
 
14. Any symptomatic or asymptomatic arrhythmia excluding sinus arrhythmia and bradycardia <math>\geq</math> 50 bps.
 
15. Use of Coumadin or Coumadin derivatives
 
16. Laboratory abnormalities in the parameters listed below:
 


	
 
a. Absolute neutrophil count <math>\leq</math> 1,000 cells/<math>\mu</math>l
 
b. Hemoglobin < 11 gm/dL
 
c. Platelet count < 125,000 cells/<math>\mu</math>l
 

Inclusion / Exclusion Criteria
	
 
d. ALT <math>\geq</math> 1.25 x ULN
 
e. AST <math>\geq</math> 1.25 x ULN
 
f. Total bilirubin > 1.0 ULN
 
g. eGFR < 60 mL/min/1.73m^2
 
17. Any vaccination within 14 days prior to 3BNC117 administration
 
18. Receipt of any therapeutic HIV vaccine in the past
 
19. Receipt of any anti-HIV monoclonal antibody in the past, or HDAC inhibitor of any kind in the past 2 years.
 
20. Participation in another clinical study of an investigational product currently or within past 12 weeks, or expected participation during this study.
 

Study Product, Dose, Route, Regimen
	
- 3BNC117 (RUhumab-001) is a recombinant, fully human monoclonal antibody (mAb) of the IgG1<math>\kappa</math> isotype that specifically binds to the CD4 binding site (CD4bs) within HIV-1 envelope gp-120.
 
- Romidepsin is an HDAC inhibitor that has emerged as one of the potent inducers of HIV-1 transcription. Romidepsin displays isoform specificity towards class I HDACs, which are particularly important to maintaining HIV-1 latency. Romidepsin will be provided by Celgene for use in this study.
 
In Group A, one intravenous infusion of 3BNC117 mAb (30 mg/kg) will be administered at week 0 and a second infusion at week 8 via a peripheral vein over 60 minutes.
 
In Groups A and B, one intravenous infusion of romidepsin (5 mg/m^2) will be administered at weeks 0, 1, and 2 (treatment cycle 1), and weeks 8, 9, and 10 (treatment cycle 2), via a peripheral vein over 120 minutes (Figure 1). In Group A, the start of each romidepsin cycle will begin 2 days after the 3BNC117 infusion.


Statistical Methodology
	
The sample size calculation is based on the primary endpoint: time to viral rebound during ATI or time to reinitiation of ART in participants who restart ART before viral rebound. Viral rebound is defined as HIV-1 RNA <math>\geq</math> 200 copies/mL on 2 consecutive measurements during ATI. If viral rebound occurs, the date of the first measurement of HIV-1 RNA <math>\geq</math> 200 copies/mL will be defined as “date of viral rebound.”
 
We will compare days from date of ART interruption until viral rebound or restarting of ART in arm A to arm B (1:1 randomization). Given a standard deviation (SD) of 10 (days), enrolling 12 patients in each of the two arms, will have 80% power to detect <math>\geq</math> 13 days (approximately 2 weeks) difference in time to viral rebound at a 5% significance level (Davey et al., 1999; Hamlyn et al., 2012; Hill et al., 2014). To accommodate for dropouts, 30 study subjects may be enrolled in the study (15 in each arm). A dropout rate of 5-15% is anticipated.
 
The number and percentage of subjects experiencing one or more AEs will be summarized by relationship to study drug and severity. AEs will also be summarized by severity grade and by relationship to study drug according to the CTCAE v4.03 (infusion-related AEs) and DAIDS Table for Grading the Severity of Adult and Pediatric Adverse Events, Version 2.0 (non-infusion-related AEs) grading scales. Changes will be calculated relative to the values collected at baseline.
 
The Wilcoxon-Mann-Whitney test will be used as primary analysis for the primary outcome. The Kaplan-Meier estimator will be used as secondary analysis to assess the magnitude of the difference between the survival curves for the two study groups. We will use the log-rank test to compare time to viral rebound during ATI in the two arms.


Statistical Methodology
	
The Wilcoxon-Mann-Whitney will be used to determine changes from baseline to the pre-ATI time-point in reservoir size for each group. Fishers exact or chi-square test will be used to compare the proportion of subjects in both groups with detectable viremia during each romidepsin treatment. Functional properties of cytotoxic T cells and NK cells will be correlated to changes in total HIV-1 DNA and IUPM. Flow cytometry data will be evaluated by Boolean partitioning of NK and T cell responses into distinct responding populations (Lamoreaux et al., 2006).
 
Finally, correlation analysis will be performed to identify the markers most likely associated with time to viral rebound. As exploratory analysis, a linear regression model will be used to determine predictors of log-transformed time to viral rebound in both arms. P values <math><0.05</math> will be considered statistically significant.

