This study will address several gaps in current knowledge: 1) The effect of combining ART+LRA+bNAb vs. ART+LRA alone on the size of the HIV-1 reservoir and time to viral rebound following ART interruption; 2) The impact of repeated exposure to a potent LRA with an interval of 2 months; 3) Correlates for time to viral rebound in patients receiving LRAs and combined LRA+bNAb; 4) The immunomodulatory effects of LRA and bNAb treatment by characterizing phenotypic as well as functional changes in antigen-presenting (DCs, macrophages/monocytes) and effector cells (NK, NKT, CD8+ cells).

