### 3.2 Hypothesis

The combined administration of two infusions of 3BNC117 (30 mg/kg) together with six infusions of romidepsin (5 mg/m^2) will prevent or delay the return of HIV-1 viremia during an analytical treatment interruption compared with administration of romidepsin alone.

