### **6.2.12 Antiretroviral and Immunogenicity Assessments**

HIV-1 levels will be assessed by (Appendix A):

1. Standard HIV-1 viral load assay (Cobas Taqman) (CLEP-certified) will be performed at a contracted laboratory, LabCorp (RUH site) and at the AUH and CUH clinical virology labs. The detection range of the assay is 20-10x10^6 copies/ml. HIV-1 viral load will be determined at multiple time points before and after 3BNC117 administration.
2. Transcription mediated amplification is a qualitative method to detect plasma HIV-1 RNA (Procleix Ultrio Plus, Genprobe). It has 50% sensitivity at 3.8 copies/mL and 95% sensitivity at 12 copies/mL. TMA results are considered binary and defined as positive or negative according to assay outcomes.
3. Single copy assay has a detection limit of 1-2 copies HIV-1 RNA/mL of plasma. This assay will be performed in the Laboratory of Molecular Immunology. This

assay will be performed on samples collected at baseline (week -2 and day 0), and 1 day after the second romidepsin infusion in each treatment cycle.

4. HIV-1 cell-associated unspliced HIV-1 RNA dd PCR assay. This assay provides an accurate quantification of HIV-1 transcriptional activity and will be performed at the AUH site. This assay has a limit of detection of 1 HIV-RNA copy per 1 million CD4+ T cells.
5. HIV-1 cell associated DNA levels in CD4+ T cells will be measured at the AUH site, before and after administration of 3BNC117. This assay has a limit of detection of 10 DNA copies per 10^6 CD4+ T cells. This assay will be performed at the AUH site.
6. The size of the functional HIV-1 reservoir will be determined by the number of infectious unit per 10^6 resting memory CD4+ T cells (IUPM) using a viral outgrowth assay before (week -2) and after therapy, just before ATI (week 22).

Given the large number of cells required for this assay, viral outgrowth assays will not be performed at a later time point. The size of the reservoir in participants who remain virologically suppressed during ATI or are re-suppressed following ART resumption will be evaluated by levels of cell-associated HIV-1 DNA, performed at week 48.

In addition, the effects of 3BNC117 on host immune responses and on circulating HIV-1 strains will be evaluated by the following assays (Appendix A):

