### 2. Size of the functional HIV-1 reservoir:

The size of the functional HIV-1 reservoir will be determined by the number of infectious unit per  $10^6$  resting memory CD4+ T cells (IUPM) using a viral outgrowth assay before (week -2) and after therapy, just before ATI (week 22). Paired student t-test or paired Wilcoxon test will be used to determine changes in reservoir size from baseline to the pre-ATI time-point for each group.

Total HIV-1 DNA, episomal HIV-1 DNA (2-LTR), and unspliced HIV-1 RNA in circulating total CD4+ T cells will also be determined at baseline (week -2, week 0), before and after each treatment cycle, at the pre-ATI time point (week 24), and at the end of the study (week 48). A 95% repeated measures ANOVA F-test will be used to compare changes in these variables during the study.

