### 4. Host immune responses:

Functional properties of cytotoxic T cells and NK cells will be correlated to changes in total HIV-1 DNA and IUPM. Flow cytometry data will be evaluated by Boolean partitioning of NK and T cell responses into distinct responding populations (Lamoreaux et al., 2006).

Finally, linear regression will be used to identify predictors of log-transformed time to viral rebound in both arms. P values  $<0.05$  will be considered statistically significant.

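### The rebound-marker and T/NK-reservoir correlations do not condition on randomised arm, so a post-treatment marker that 3BNC117 shifts can appear to predict rebound only because it tracks the arm

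*Combined protocol and SAP*

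**What the plan says.** Three analyses are involved.

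- **Correlation with rebound time** (Study Schema, Statistical Methodology only): "correlation analysis will be performed to identify the markers most likely associated with time to viral rebound". Treatment arm is not mentioned.
- **Regression of log rebound time.** The Schema labels it exploratory and says "a linear regression model will be used to determine predictors of log-transformed time to viral rebound in both arms". Section 8.1 (Host immune responses) says "linear regression will be used to identify predictors of log-transformed time to viral rebound in both arms". No covariates are listed. The reference to both arms could mean one pooled model or a separate model in each arm.
- **T/NK function against reservoir change** (Schema and 8.1): "Functional properties of cytotoxic T cells and NK cells will be correlated to changes in total HIV-1 DNA and IUPM". Arm is again not mentioned.

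Both places then declare P values below 0.05 statistically significant.

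The question behind these analyses is one of four knowledge gaps in section 3.1.1: "Correlates for time to viral rebound in patients receiving LRAs and combined LRA+bNAb". The hypothesis in 3.2 is that adding 3BNC117 "will prevent or delay the return of HIV-1 viremia during an analytical treatment interruption compared with administration of romidepsin alone". Section 6.2.12 states that "the effects of 3BNC117 on host immune responses and on circulating HIV-1 strains will be evaluated by the following assays", and it includes T- and NK-cell measurements before and after each treatment cycle.

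**The concern.** Section 3.1.1 asks which markers go with rebound time among patients on each regimen. The matching null hypothesis is no association between marker and rebound time given the arm. A correlation over all participants, or a regression without an arm term, tests a different null: no association in the two arms combined. That second null is false whenever 3BNC117 changes both the marker and the rebound time, even if the marker says nothing about rebound within either arm.

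The trial hopes for the first change and sets out to measure the second. If it succeeds, a pooled marker analysis partly repeats the comparison of arm A with arm B, and bystander markers could be reported as correlates of rebound. The opposite error is also possible: a real within-arm correlate that the antibody shifts against its own direction can be hidden.

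This is separate from testing many markers and from censoring. It arises with a single, fully observed marker.

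**Working it through.** **Inputs from the plan.** Section 8.2: 12 per arm, SD 10 days, difference 13 days, 5% level, 80% power, Wilcoxon-Mann-Whitney test by the minimum asymptotic relative efficiency method. Section 3.1.1: rebound within 2–3 weeks in most subjects off ART.

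**Assumptions.** The documents give no expected effect of 3BNC117 on any marker, so the marker shift δ (in within-arm SDs) is varied. Tests are two-sided. Control mean rebound time is 17.5 or 21 days where a log scale needs one.

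**The plan's own figure.** With d = 13/10 = 1.3, n per arm multiplied by 0.864 and a noncentral t, power is 80.1%. The stated 80% is reproduced. The plan gives no figure for the marker analyses.

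**Why pooling creates a correlation.** Let marker and rebound time be independent within each arm, with arms of equal size. The pooled covariance, in SD units, is 0.25 × δ × 1.3. The pooled variances are 1 + 0.25δ² for the marker and 1 + 0.25 × 1.69 = 1.4225 for time. Hence

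r = 0.325δ / √[(1 + 0.25δ²) × 1.4225].

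- δ = 0.5: r = 0.1625 / √(1.0625 × 1.4225) = 0.13
- δ = 1: r = 0.325 / √(1.25 × 1.4225) = 0.24
- δ = 2: r = 0.65 / √(2 × 1.4225) = 0.39

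The within-arm correlation is zero in every case.

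**How often that tests as significant.** Simulation with 40,000 trials per cell, 12 per arm, marker unrelated to rebound within arm:

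| Setting | δ = 0 | 0.5 | 1 | 2 |
|---|---|---|---|---|
| 13-day effect, pooled, days | 4.9% | 9.3% | 21.5% | 50.8% |
| 13-day effect, pooled Spearman | 5.1% | 9.5% | 22.1% | 53.2% |
| 13-day effect, pooled, log time (lognormal, control mean 21) | 5.2% | 10.3% | 24.5% | 57.7% |
| 7-day effect, pooled, days | 5.0% | 6.8% | 10.7% | 20.1% |
| No arm effect, pooled, days | 4.8% | 5.0% | 5.1% | 5.1% |
| 13-day effect, arm in model | 5.1% | 5.2% | 5.0% | 4.9% |

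A second simulation (2,000 trials per cell) used gamma or truncated-normal times, control mean 17.5 days and rounding up to weekly visits. At 13 days it gave 8–10%, 20–24% and 48–55% for the three shifts. At 7 days and a 1 SD shift it gave 11–12%. With 15 per arm and a 13-day effect, the days-scale pooled rates are 10.9%, 26.5% and 60.7%.

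**Masking.** Gamma times, 12 per arm, 13-day effect, marker raised 1 SD by 3BNC117:

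- Within-arm correlation −0.6: power 7–8% pooled, against 79–82% conditioned on arm.
- Within-arm correlation +0.6: power 97% pooled, against 84% conditioned on arm.

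Pooling therefore hides a correlate in one direction and inflates it in the other.

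**Price of adjusting.** Residual degrees of freedom fall from 24 − 2 = 22 to 24 − 3 = 21. The pooled marker variance is 1 + δ²/4 times the within-arm variance, so the marker coefficient's variance rises by about that factor: 1.25 at δ = 1 and 2.0 at δ = 2.

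No figure was computed for T/NK function against reservoir change. That would need an assumed arm effect on the reservoir, which was not modelled.

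**The case against.** **The plan is unspecified, and that does not make it pooled.** A reader might infer that all the marker analyses omit arm by design. The documents do not support that. For the regression, the reference to both arms may mean one fit per arm, which would suit the gap stated in 3.1.1, and the problem would then not arise there. Against this, the Schema describes a single model, and for within-arm work section 8.1 uses other wording ("changes in reservoir size from baseline to the pre-ATI time-point for each group"). The text does not settle it. The two correlation analyses have no such wording to fall back on.

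**Not every marker is exposed.** Baseline IUPM and HIV-1 DNA are balanced by randomisation apart from chance. Both arms receive romidepsin, so its effects on immune markers are shared. At week 24, 112 days after the second infusion, the half-lives in 3.1.2.3 leave 2^(−112/17.6) = 1.2% of the antibody, or 0.03% at 9.6 days, so a large shift lasting to the pre-ATI samples is not established. These points stand. They limit the concern to post-treatment markers and make the size of the shift an assumption.

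**Antibody level is not a fair worst case.** A reader might expect the most extreme false-positive rates from 3BNC117 concentration, which would be near zero in arm B. Section 6.2.13 plans that measurement in Group A only, so it cannot enter a pooled correlation.

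**A marginal association can be a legitimate target.** If the antibody works through a marker, conditioning on arm removes part of the signal. With a 13-day delay acting wholly through a marker shifted 3 SD, power is 97% pooled and 55% with arm; at 2 SD it is 99.8% and 95%. This stands against making the adjusted result the only one. It does not justify a pooled result alone, which cannot distinguish a mediator from a bystander.

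**The consequence is limited.** The Schema calls the regression exploratory, and correlates of rebound are not a listed objective or endpoint in 3.3 to 3.6.

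**Conclusion.** The concern holds for post-treatment markers. The two correlation analyses state no conditioning on arm, and the regression is ambiguous. Under the plan's own design figures, a marker unrelated to rebound within either arm would be flagged by a pooled test about 10%, 20–25% and 50–55% of the time for shifts of 0.5, 1 and 2 SD (48–58% at 2 SD across the regression models and Spearman results shown). At a 7-day effect and a 1 SD shift the rate is about 11–12%. It stays near 5% if there is no arm effect on rebound or no marker shift. The shifts are assumptions, and the result depends on 3BNC117 actually delaying rebound.

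A reader might go further and conclude that the primary result or the baseline predictors are compromised. Neither follows: the Wilcoxon-Mann-Whitney comparison of arms does not use the markers, and randomisation protects baseline values apart from chance. For T/NK function against reservoir change the same reasoning applies if 3BNC117 moves both, but its size is unknown. This is a change worth making before analysis; it does not threaten the trial's main conclusion.

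**What to change.** In the Study Schema and section 8.1, state for post-treatment markers:

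1. The main result conditions on randomised arm: arm as a covariate in the regression of log rebound time, and a within-arm or partial Spearman coefficient for the correlations, including T/NK function against change in HIV-1 DNA and IUPM.
2. The pooled, unadjusted result is reported beside it and labelled as including the between-arm difference, so that a possible mediator is not lost.
3. Markers measured only in arm A, such as 3BNC117 level and anti-3BNC117 antibody, are analysed within arm A.
4. Whether the regression is one model or one per arm is stated explicitly.

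This needs a few sentences and no new data. It costs one residual degree of freedom and a loss of precision for markers strongly shifted by arm, by a variance factor of about 1.25 at 1 SD and 2.0 at 2 SD.
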